#### 6.2. Secondary outcome analysis

Despite our pre-randomization chart review, we anticipate that some patients will be randomized in error. These patients were determined to be ineligible based on information about a health condition that preceded randomization. For this reason, we will report our primary outcome excluding patients who were randomized in error. In additional two secondary per-protocol analyses are planned, one that excludes patients who were determined ineligible because they moved, or clinical reasons that occurred post-randomization (These patients may have their referral canceled after the pre-procedure visit with the GI and a clinical review of their medical history.); and a second that additionally excludes patients who were never reached by the navigator. Other secondary analysis will assess between-group differences in time to colonoscopy completion. Using the pathology report, we will also track colonoscopy-related quality measures, including adequacy of colonoscopy prep, detection of adenomas and cancer, and cancer stage at detection.

We will use the Cox proportional hazards regression model with shared frailty for time to colonoscopy completion. The shared frailty model is the survival data analog to random effects regression models that can account for the clustering effect of patients within clinics and Efron method to handle tied survival times. The independent variable will be study arm, which will be coded the same as in the primary outcome analysis. Significant hazard ratios >1 indicate that patient navigation has shorter times to colonoscopy completion and/or initiation of cancer treatment than usual care. For binary secondary outcome and process measures (e.g. time to colonoscopy receipt, adequacy of bowel prep), we will use the same modeling framework (e.g., multilevel logistic regression) as described for our primary outcome. (See Handling of Deviations and Protocol Amendments 9.5)

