## 3. Randomization and blinding

Patients meeting clinical eligibility criteria will be randomized by the health center (Sea Mar) analyst to receive either the patient navigation intervention or usual care. Study identification numbers linked to patients will be uploaded into REDCap® on a weekly basis, for patients in the navigation arm, with date of abnormal FIT result. We anticipate that the time between patient identification and study randomization will take about 2 weeks. (See **Handling of Deviations and Protocol Amendments 9.4**)

Randomization will be performed using a stratified approach that considers patients' county of residence. We will use Sealed Envelope (London, UK) to randomize patients 1:1 to navigation or usual care in blocks of 4 to 8 individuals, stratified on county of residence. For practical reasons, neither the research team nor the clinic staff will be blinded to randomization assignment. However, measures have been taken to preserve as much blinding as possible. Staff trained in navigation will not perform colonoscopy referral coordination (as part of usual care). Patients randomized to patient navigation are removed from the referral coordinator list to eliminate potential outreach by referral coordinators. In this way, the patient navigation intervention will not be overlaid on usual care, as doing so would result in multiple contacts from multiple clinic staff. (Consistent with usual care, referral

coordinators will contact referred patients who have not completed a colonoscopy making up to three phone attempts; patients who are not reached will be sent a letter.)

The randomization will result in 600 patients assigned to the patient navigation arm and 600 assigned to the usual care arm. We will assess rates of colonoscopy receipt at 1 year overall, and will perform a heterogeneity of treatment effect analysis to assess differential effects by age, sex, ethnicity, language preference, insurance status, and probability of adherence (based on the risk model), using data from the electronic health record.

CHR analysts will assign a colonoscopy completion probability, based on the risk prediction model. These methods have been described previously.

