#### 6. Statistical Methods

#### 6.1. Primary outcome analysis

Primary analysis will rely on a modified intention-to-treat (ITT) that excludes patients from both arms who are randomized in error (determined to be ineligible based on information in the medical record that was missed during the eligibility determination process). Patients in the primary ITT data analysis will retain their randomization assignment irrespective of whether they received patient navigation. Two secondary per-protocol analyses are planned: one that excludes patients who were determined ineligible because they moved, or clinical reasons that occurred post-randomization; and a second that additionally excludes patients who were never reached by the navigator.

Sea Mar's EHR data will be transferred to CHR every 6 months via a secure file transfer. We will examine the distribution of all variables prior to analyses and verify all missing and out-of-range values. We will assess the ICC. If the ICC is .001 or above, we will use hierarchical generalized linear modeling to account for clustering of patients within clinics. If the ICC is less than .001, we will use adjusted logistic regression without accounting for clustering to optimize parsimony. Because the primary outcome is binary (i.e., follow-up colonoscopy, yes/no), we will use a model with a logit link and binomial distribution (i.e., multilevel logistic regression). The independent variable will be arm (dummy-coded) with usual care as the reference group. 'Clinic' will be modeled as a random effect. The model will include county as a covariate (fixed effect) as it was a stratification factor for randomization.

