# 7. Data auditing and validation

# Fidelity assessment and intervention dose (scientific rigor).

Our fidelity assessment will be designed in accordance with established methods outlined by the NIH Behavior Change Treatment Fidelity Workgroup and will focus on: (1) the accuracy of data capture for our primary and secondary outcomes (measurement fidelity), and (2) rigor and consistency with which the intervention is delivered (intervention fidelity). As part of intervention fidelity, we will assess the intervention dose. Intervention fidelity: To address intervention fidelity, research staff will monitor navigator calls with patients and provide feedback. A quality assurance tracker will be used by research staff to track content and timing of calls and identify areas for improvement. Any issues will be addressed during debrief meetings and booster training sessions.

- During the pilot, research staff will listen to a portion of patient calls for navigator coaching purposes.
- During the main trial, research staff will listen to 10 live calls every 3 months for the first year, and then 10 live calls every 6 months during the second year.

Qualitative patient interviews at the end of the program (n = 60) will gather patient-reported information on receipt of each call type, consistent with the NHCRCSP.

Intervention dose. As part of the fidelity assessment, we will track consistency of intervention dose: the number and content of phone calls delivered by patient navigators based on data collected from the patient navigation tracking system designed in REDCap®. The standard protocol includes six timed phone calls that address predefined content areas; thus, dose will be calculated as the proportion of phone calls completed and/or content areas addressed (with 6 as the denominator).

| NAVIGATION PROTOCOL TOPIC AREAS                   | COMPLETE IF DELIVERED BY  |  |
|---|---|--|
| Topic 1 – Introductory Call                       | Within 1-7 days of navigator assignment                           |  |
| Topic 2 – Barrier Resolution Calls                | Flexible timing prior to procedure                                |  |
| Topic 3 – Bowel Prep Review Call                  | 5-7 days before colonoscopy                                       |  |
| Topic 4 – Day before Colonoscopy Check-In
Call | Afternoon or evening before colonoscopy (text message acceptable) |  |

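### The first per-protocol analysis excludes patients on post-randomization findings that the two arms have unequal chances of producing, with no blinded or common rule for deciding them

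*SAP*

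**What the plan says.** The primary set is defined in SAP 6.1: "Primary analysis will rely on a modified intention-to-treat (ITT) that excludes patients from both arms who are randomized in error". Patients who move or become unsuitable later stay in it.

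Two secondary per-protocol analyses follow. The first is "one that excludes patients who were determined ineligible because they moved, or clinical reasons that occurred post-randomization". SAP 6.2 adds how this can come to light: "These patients may have their referral canceled after the pre-procedure visit with the GI and a clinical review of their medical history". The other is "a second that additionally excludes patients who were never reached by the navigator", so it starts from the first set and removes more. The first rule is worded without reference to arm.

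Contact is unequal by design. For navigation, SAP 7 states: "The standard protocol includes six timed phone calls that address predefined content areas". These calls are logged in a REDCap tracking system, and SAP 3 describes the weekly REDCap upload for navigation-arm patients. For usual care, SAP 3 says that "coordinators will contact referred patients who have not completed a colonoscopy making up to three phone attempts", followed by a letter to those not reached. The same section says that "neither the research team nor the clinic staff will be blinded to randomization assignment".

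SAP 5.1 accepts that navigated patients probably have more complete capture of colonoscopies. It answers with an arm-blinded abstractor and with requests for procedure and pathology reports for every patient lacking evidence of a colonoscopy in the health record. Neither document describes a comparable process for deciding who moved or became ineligible.

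**The concern.** A patient whose referral is canceled, or who has left the area, will rarely have a colonoscopy on record. Excluding such patients removes failures from the denominator. That does little harm under no effect if both arms lose the same share, but the share depends on someone finding out.

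A navigated patient who has moved may be identified on a call and logged. A similar usual-care patient may never answer three calls and a letter, stay unclassified, and count as a failure. The SAP already applies this reasoning to the outcome but does not carry it over to the exclusions.

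At stake is how a secondary result is read. A per-protocol estimate above the primary one could be taken as the effect among patients able to have the procedure, when part of the gap reflects who was classified as unable.

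**Working it through.** **Inputs.** From the SAP: 44% usual-care completion, 600 patients per arm, and a smallest detectable difference of 9.2 points without a design effect (SAP 3 and 4). The documents give no exclusion rates, so those below are assumptions. There is no plan figure for these exclusions to reproduce. The 9.2 points serve only as a yardstick; the matching odds ratio checks, (0.532/0.468)/(0.44/0.56) = 1.45.

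**Formula.** If a share x of an arm is excluded and all of them are non-completers, the completion rate becomes p/(1 - x). With the same true p in both arms, the spurious difference (navigation minus usual care) is p/(1 - x_N) - p/(1 - x_U).

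**No true effect, p = 44% in both arms:**

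| Excluded, navigation | Excluded, usual care | Rate, navigation | Rate, usual care | Difference (points) |
|---|---|---|---|---|
| 5% | 5% | 44/95 = 46.3% | 44/95 = 46.3% | 0 |
| 5% | 4% | 44/95 = 46.3% | 44/96 = 45.8% | +0.5 |
| 8% | 4% | 44/92 = 47.8% | 44/96 = 45.8% | +2.0 |
| 10% | 3% | 44/90 = 48.9% | 44/97 = 45.4% | +3.5 |
| 5% | 10% | 44/95 = 46.3% | 44/90 = 48.9% | -2.6 |

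In patients, the 8% vs 4% row removes 48 and 24 of 600 and leaves 264/552 against 264/576. Over this range the bias is about half a point for each percentage point by which exclusions differ.

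**Against the yardstick.** 2.0/9.2 = 22% and 3.5/9.2 = 38% of the detectable difference. At 10% vs 5%, in either direction, a nominal 5% test rejects a true null about 14% of the time (normal approximation, clustering ignored).

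**With a true 9.2-point effect (53.2% vs 44%).** Excluding 10% of navigation and 5% of usual care gives 53.2/90 - 44/95 = 59.1% - 46.3% = 12.8 points. Reversing the shares gives 53.2/95 - 44/90 = 56.0% - 48.9% = 7.1 points.

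**If some excluded patients had completed.** Suppose one in ten had, at 8% vs 4%: (44 - 0.8)/92 - (44 - 0.4)/96 = 47.0% - 45.4% = +1.5 points. The table therefore shows the largest bias for each pair of rates.

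**The case against.** A reader might infer that this analysis is bound to favor navigation, and so would show a benefit where none exists. The documents do not support that:

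- They give no exclusion rates by arm, and the rule applies to both arms.
- Usual-care coordinators also call patients who have not completed, and may learn of moves or cancellations.
- If usual-care patients complete later or less often, more of them remain at risk of moving or becoming unsuitable first, which could reverse the sign.
- The route through the pre-procedure visit creates imbalance only if navigation changes attendance at that visit, which sits awkwardly with a strict null. Detection through navigator calls does not need that, but the remark in SAP 6.2 mentions the visit and the clinical review, not the calls.

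A reader might also infer that the primary result is compromised, or that exclusion here is possible in one arm only. Neither follows. The primary set keeps these patients, and the one-arm rule (never reached by the navigator) belongs to the other per-protocol analysis.

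It is also fair to say that clinical review before randomization (SAP 2; Protocol Modifications table) should keep this group small, and that no decision is tied to a secondary analysis. A blinded abstractor cannot equalize what unblinded staff happened to record.

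These arguments remove any certainty about direction and limit the size. They do not supply a common procedure for deciding the exclusions, and an imbalance in either direction distorts the estimate.

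**Conclusion.** The concern holds as a risk of unequal removal of non-completers, plausibly more from navigation, with the direction open. Under no true effect and with all exclusions non-completers, the bias runs from 0 at equal rates to +2.0 or +3.5 points when navigation loses 4 or 7 percentage points more, and to about -2.6 points when usual care loses 5 more. All the exclusion rates are assumed. The primary modified intention-to-treat analysis is not touched by this exclusion. The second per-protocol analysis carries the problem forward, in addition to its own one-arm rule. The SAP should be changed on this point, but the trial's main conclusion does not depend on it.

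**What to change.** In SAP 6.1 and 6.2, have the arm-blinded abstractor already planned in SAP 5.1 decide these exclusions:

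- Apply one written rule to all patients in both arms, defining what counts as a move or a clinical reason.
- Use only sources sought with equal effort in both arms: the health record and requested GI records. Do not use navigator logs. The requests would have to reach beyond procedure and pathology reports, since a referral canceled before the procedure produces neither.
- Report the number excluded and the reason, by arm.
- Label the analysis supportive and state that differences in what staff recorded can remain.
- Rest the efficacy conclusion on the modified intention-to-treat analysis, which counts these patients as non-completers unless a colonoscopy is found.

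The cost is a few sentences in the SAP, a little more abstraction work, and a narrower secondary analysis.

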## 6.3. Analysis of possible moderators

Our preliminary data showed follow-up colonoscopy receipt varied substantially by probability strata (30%, 59%, and 93% for the low, moderate, and high strata, respectively), suggesting that assessments of clinically meaningful impacts could differ by probability strata. To determine whether adherence probability moderates the effect of the intervention, we will add probability strata (moderate, low vs. high) and the product of stratum and arm to the primary outcome model. The product represents the interaction of arm and probability stratum; a significant term provides evidence for effect modification. We will determine the nature of any interaction by examining the simple main effects using graphical methods. We will repeat this analysis using the continuous risk score in place of the risk strata. We will have 80% power to detect an odds ratio for the product term, which represents the multiplicative change from the odds ratio for the moderate probability stratum for arm compared to the low probability stratum for arm of 2.98 (or 0.34 in the opposite direction), accounting for the design effect, and 2.17 (or 0.46 in the opposite direction) assuming no design effect, at a two-tailed alpha level of .05. Previous literature has reported significant differences in the effectiveness of patient navigation for colorectal cancer screening across patient subgroups defined by:

- Sex (patient navigation will be more effective in women vs. men)
- Preferred language (patient navigation will be more effective in patients who preferred Spanish vs. English; participants who indicated other will not be included in this analysis
- Age (patient navigation was more effective in younger vs older age groups, defined as (50–54, 55–59, 60–64, 65–69, and 70–75)
- Hispanic ethnicity (patient navigation will be more effective in Hispanic patients vs. non-Hispanic patients)
- Insurance status (patient navigation will be more effective in uninsurance adults vs. insured adults)
- Probability of patient adherence to colonoscopy without navigation (patient navigation will be more effective in patients having lower probability of adherence, based on risk score)
- See Handling of Deviations and Protocol Amendments 9.6

We will perform separate analyses for each patient moderator. Because the examination of the moderating effects of patient characteristics is secondary and exploratory, this study is not formally powered for these analyses. Given the inherent lower power of moderator analyses, we will focus on the magnitude of product term coefficients.

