## 5.3. Potential moderators of effectiveness

The following variables will be tested as potential moderators of effectiveness:

| Potential Moderator                 | Categories   |
|-------------------------------------|--|
| Sex                                 | Male, female   |
| Preferred language                  | English, Spanish, Other                              |
| Age                                 | 50–54, 55–59, 60–64, 65–69, and 70–75                |
| Insurance status                    | Medicaid, Medicare, self-pay (uninsured), commercial |
| Probability of patient adherence to | Low: 0 < .52, Moderate: .52 < .63, High: ≥.63)       |
| navigation (based on risk score)    |  |

- sex (patient navigation will be more effective in women vs. men)
- preferred language (patient navigation will be more effective in patients who preferred Spanish vs. English; participants who indicated other will not be included in this analysis
- age (patient navigation was more effective in younger vs older age groups, defined as (50–54, 55–59, 60–64, 65–69, and 70–75)
- Insurance status (patient navigation will be more effective in uninsurance adults vs. insured adults)
- Probability of patient adherence to colonoscopy without navigation (patient navigation will be more effective in patients having lower probability of adherence, based on risk score)
- See Handling of Deviations and Protocol Amendments 9.6

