#### 8. Handling of Deviations and Protocol Amendments

- 8.1. Included all patients ages 50-75 with an abnormal FIT result, eliminated requirement of having moderate or high risk of follow-up colonoscopy non-adherence. Given the relatively low colonoscopy completion probability in the highest quintile group (65% vs. 93% estimated), we plan to randomize all eligible abnormal FIT patients. We will still prospectively calculate the patients' estimated probability of obtaining a colonoscopy, using the risk prediction model and preform subgroup analysis considering risk level as a moderator of effectiveness.
- 8.2. Eliminated cost and cost-effectiveness analysis. These analyses were eliminated because of COVID-19 resources constraints; through an official request to NCI dated 3/1/2021.
- 8.3. Eliminated no show/canceled appointments as a secondary outcome. We eliminated as an outcome noshow/canceled appointments because the number of referring GI practices would lead to inconsistencies and inaccuracies in the collection of these data.
- 8.4. Changed the randomization process. Following an electronic health record conversion, the original automated randomization in place at the partnering health center was disabled. As a result, from August 2021 through April 2022, patients were randomized weekly using the SURVEYSELECT procedure in SAS (Cary, NC).
- 8.5. Used Restricted Mean Survival Time for time-to-event analysis. To assess differences in time to colonoscopy completion between study arms (secondary outcome), we originally planned to use Cox proportional hazards and median survival time. Instead, we computed the log-rank test and restricted mean survival time (adjusted for county). Restricted mean survival time provides estimates of the mean time to event regardless of event rate whereas conventional median survival time is only computable when the event rate is 50% or greater. Moreover, restricted mean survival time is a more direct and interpretable measure of actual survival time, compared to a hazard ratio derived from a Cox model.
- 8.6. Added county and eliminated Hispanic ethnicity as potential moderators. County (8 unique counties in WA State) was added as a potential moderator, given possible variation by county in GI provider waittimes and other factors. We also eliminated Hispanic ethnicity as a moderator as it has a strong correlation with preferred language.

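### SAP 6.3 takes a significant product term as evidence of effect modification and names no joint interaction test; read term by term, the false-positive rate is about 9% to 23% for moderators with 3 to 8 levels

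*SAP*

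**What the plan says.** For adherence probability, SAP 6.3 states: "we will add probability strata (moderate, low vs. high) and the product of stratum and arm to the primary outcome model". With three strata and high as the reference, that is two product terms. The criterion follows: "a significant term provides evidence for effect modification". The accompanying power statement is made "at a two-tailed alpha level of .05". The section then adds a second version of the same analysis: "We will repeat this analysis using the continuous risk score in place of the risk strata". Protocol section 7a carries the same criterion for the probability strata.

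The end of SAP 6.3 says that each moderator is analysed separately, that the work is secondary and exploratory, and that the trial is not formally powered for it. It continues: "Given the inherent lower power of moderator analyses, we will focus on the magnitude of product term coefficients".

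The moderators are listed in SAP 5.3 and amended in SAP 8.6:

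- Sex has two levels. Language has two as analysed, because the Other group is left out.
- Probability has three levels.
- Insurance is tabulated as "Medicaid, Medicare, self-pay (uninsured), commercial", although the hypothesis beneath the table compares uninsured with insured adults.
- Age has five bands, with a younger-versus-older hypothesis.
- SAP 8.6 drops Hispanic ethnicity and adds an eight-level factor: "County (8 unique counties in WA State) was added as a potential moderator". No direction is stated for it.

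Neither document gives a joint test of the product terms, an interval requirement for them, a reference category for age, insurance or county, or a statement on multiplicity across moderators.

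**The concern.** A moderator with k levels contributes k − 1 product terms against a reference level. If any one of them at p < 0.05 counts as evidence, the error rate for that moderator exceeds 5% and grows with k. It also depends on which level is the reference, a choice with no scientific content. The SAP's own probability analysis shows the ambiguity. The model uses high as the reference, but the power statement concerns moderate versus low, which is the difference between two of its coefficients.

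Emphasis on coefficient size raises a related difficulty. In small levels the estimates vary widely, so the most striking coefficient tends to be a noisy one unless its interval is read with it.

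The Protocol background presents the study as a way to learn which patients most need navigation. A chance finding for one county or age band could be carried into advice on where to place navigators.

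**Working it through.** **The plan's own figure.** SAP 6.3 gives a detectable product-term odds ratio (OR) of 2.17 without a design effect, at 80% power. For a ratio of two odds ratios, solve ln(OR) / √Σ[1/(n·p·q)] = 1.960 + 0.842 = 2.802 over the four arm-by-stratum cells, with usual-care rates of 30% and 59% (SAP 6.3) and no arm effect in the low stratum. Stratum sizes are not given, so n per cell is an assumption:

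- n = 200 gives 2.39 (2.31 in the opposite direction, as a reciprocal).
- n = 240 gives 2.21 (2.15).
- n = 300 gives 2.02 (1.98).

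The stated 2.17 is consistent with about 240 per cell. It implies a standard error of ln(2.17)/2.802 = 0.775/2.802 = 0.277 for one term. It is a single-contrast figure and does not describe a rule over several terms.

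**Inputs.** 1200 patients randomized 1:1 (SAP 3); 44% completion in usual care and about 53% with navigation (SAP 4); level counts from SAP 5.3 and 8.6. Assumptions: equal level sizes, no true interaction, no design effect.

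**Formulas.** Let L_j be the arm log odds ratio in level j, with n_j patients per arm.

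- v_j = 1/(n_j·p0·q0) + 1/(n_j·p1·q1).
- Product term b_j = L_j − L_ref, with variance v_j + v_ref.
- With equal sizes any two terms correlate 0.5, because they share the reference.
- Per-term rule: at least one |b_j|/SE > 1.96.
- Joint rule: Wald chi-square on k − 1 df.

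Age: n_j = 1200/5/2 = 120. v = 1/(120×0.44×0.56) + 1/(120×0.53×0.47) = 0.0338 + 0.0335 = 0.0673, so the SE of a term is √(2×0.0673) = 0.367.

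County: n_j = 1200/8/2 = 75. v = 0.0541 + 0.0535 = 0.1076, so the SE is √0.2153 = 0.464.

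**Results** (400,000 null draws). The last column is the median of the largest product-term OR, in either direction.

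| Moderator | Levels | Terms | Per-term rule | Joint test | Median largest OR |
|---|---|---|---|---|---|
| Sex; language | 2 | 1 | 5.0% | 5.0% | 1.17 |
| Probability strata | 3 | 2 | 9.1% | 5.0% | 1.33 |
| Insurance, four categories | 4 | 3 | 12.6% | 5.0% | 1.47 |
| Age | 5 | 4 | 15.6% | 5.0% | 1.61 |
| County | 8 | 7 | 22.9% | 5.0% | 2.01 |

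A binomial simulation of whole trials (100,000 each) gave 9.1%, 13.2%, 15.4% and 24.9% for the per-term rule at 3, 4, 5 and 8 levels, and 4.8% to 5.0% for the joint test. For three levels, direct integration of the bivariate normal with correlation 0.5 also gives 9.1%.

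**Sensitivity.** With the SAP's stratum rates (30%, 59%, 93%), the probability figure is 7.9% with high as reference and 9.4% with low. With assumed unequal county sizes (8:4:3:2:1:1:1:1), it is 29% with the largest county as reference and 19% with the smallest; across the size patterns tried, the range was roughly 18% to 29%. Only relative variances enter these rates, so a common design effect leaves them unchanged, though it would widen the chance spread of the coefficients.

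**Chance size.** With no interaction, the largest age term lies beyond 1.5 in either direction in 64% of trials, and the largest county term beyond 2 in 51%.

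**Across moderators.** With six joint tests at 5%, treated as independent: 1 − 0.95^6 = 0.2649, about 26%.

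**The case against.** The criterion is written for the probability strata and speaks of the product in the singular. It could mean the interaction as a whole, and it is not restated for age, insurance or county. A reader might infer that the plan declares effect modification for every moderator as soon as any one term is significant. That wording is not in the SAP. It is the natural reading of a model with several terms and no joint test, but it is a reading, so the rates above are conditional on it.

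For the one moderator that the sentence governs, the inflation is under twofold, and the repeat with the continuous risk score is already a 1-df test with no reference category. Insurance may be meant as a two-group contrast, which has one term and no inflation. The age hypothesis is directional, so an isolated significant middle band would not support it.

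A reader might also infer that coefficient size is a second decision rule with its own false-positive rate. The SAP says only "we will focus on the magnitude of product term coefficients". It sets no threshold and selects no largest term, so no error rate can be attached. The sentence can fairly be read as a move from testing towards estimation. What remains is that no interval is required alongside the estimate.

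The exploratory label lowers the stakes. It does not say which test is to be used, and it leaves the arithmetic unchanged.

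**Conclusion.** The point holds in a limited form. No joint interaction test is specified. Read per term, the stated criterion gives about 9% for probability strata, 13% for insurance in four categories, 16% for age and 23% for county (roughly 18% to 29% with assumed unequal sizes), against 5% with a joint test. The excess is under twofold at three levels, about threefold for age and about fourfold to fivefold for county. Sex, language and the continuous risk score are not affected.

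These figures rest on reference coding, assumed level sizes and no true interaction.

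It is tempting to quote one overall figure. If the per-term rule applied to all six moderators and they were independent, about 53% of null trials would show something, or 49% with two-group insurance. The documents do not support that as a headline, because the rule is stated only for the probability strata and the insurance coding is open.

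The change is recommended because it is cheap. The primary analysis is not touched.

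**What to change.** In SAP 6.3:

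1. For each moderator with more than two levels, replace the significant-term criterion with one joint likelihood-ratio or Wald test of all arm-by-level terms, on levels minus 1 df. Where the hypothesis is directional, a single prespecified 1-df contrast or trend may be used instead: younger versus older age, uninsured versus insured, or the continuous risk score.
2. State the coding of insurance, and the reference category for each factor.
3. Report every product term and every stratum-specific effect with a 95% confidence interval, and interpret coefficient size only with its interval.
4. State that the six moderator tests are not adjusted for each other, and that about 26% of trials with no interaction would still show at least one nominal finding if the tests are independent. The joint test corrects the error rate within a moderator, not across moderators.

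A random arm-by-county effect is not required. Eight counties carry little information about such a variance, and the joint 7-df test is sufficient.

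The cost is a few sentences and one extra test statement per model, with no new data. Fewer nominal subgroup findings will be reported.
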